We aim to conduct a single-center randomized controlled trial to measure the impact of physical activity through virtual reality video games on the motor and cognitive performance of youth with MS. Through such a home-exercise program coupled with patient online behavior counseling, we hypothesize that we can significantly impact subjective and objective measures of disease disability in this MS age population.

Objectives

Primary objective: to assess the impact of a virtual reality video (VR) game exercise program on **objective cognitive assessments in youth with MS** (measures outlined below). The **null hypothesis** for this study is that there is no difference in the **Brief Cognitive Assessment for MS** in cognitive disability of youth with MS between those enrolled in a 6-month VR active video game program and those with routine follow-up care. The alternative hypothesis is that there is a difference in measures of cognitive disability between the two groups (two-sided hypothesis).

Secondary objectives:

- To determine the impact of VR physical activity on subjective measures of cognitive, physical and psychosocial disability in youth with MS
- To determine the impact of VR physical activity on the 6-Minute Walk Test (6MWT).

- To determine the number of clinical relapses and new T2 MRI lesions (brain)
- To determine the **safety** of implementing a VR active video game program at home
- To evaluate the effect of VR exercise programs on overall behavior towards physical activity and health promotion in youth through self-report questionnaires

Study Design

- **Single-center, single blinded, randomized controlled trial** comparing a 6-month VR active video game intervention with standard management of physical activity in youth with MS.
- Each participant will be randomly allocated to either the intervention group or the control group for a **period of 6-months** with pre- and post- assessments performed at onset, 3 months, 6 months and 12 months follow-up.
- The study will be conducted over one year with 6 months of intervention. Each group will include 12 subjects (**total subjects = 24**).
- The Microsoft VR active game program will consist of 3 weekly sessions of 45 minutes each combining 3 different types of exercise (cardiovascular and strength with 'Box VR', flexibility with 'Beat Saber', coordination with 'The Climb').

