- To assess the impact of the VR exercise program, a series of subjective and objective assessments will be performed prior to onset, at 3 months, upon completion at 6 months and at 12 months follow-up. These assessments are detailed in the section 'Study procedures' below.
- **Assessment of safety** will be conducted throughout the intervention and will consist of self-reported incidents that occur during the exercise sessions, including falls or physical injuries. These events will be recorded at 1 month, 3 months and 6 months from onset by the investigators.
- **Assessment of adherence** to the program will be documented throughout the study via anonymized exercise logs provided by Microsoft that will monitor participation and overall performance for each game. Microsoft will also provide customer service for any technical difficulties with the VR headsets provided.
- **Personal sessions** with each participant in the intervention group will be conducted via phone calls to educate them on the importance of exercise and assess for any difficulties to adhere to sessions. They will take place at 1 month, 3 months and 6 months. Furthermore, a survey questionnaire will be given to all participants enrolled in the intervention group at the 6-month follow-up time to determine the degree of incorporation of physical activity into their daily life following completion of the study.

Study Population

- Inclusion criteria: (1) **age between 15-25 years**, (2) **confirmed diagnoses of Pediatric-Onset MS (<18 years)** according to the 2017 revised McDonald criteria (relapsing-remitting), (3) **Expanded Disability Status Scale (EDSS) ≤ 5.0**, (4) **relapse free for the past 30 days**, (5) **no contraindications to physical activity**, including pregnancy (6) no history of visual provoked seizures and (7) participant and parent (if between 15 and 18 years of age) **written informed consent**.
- The participants will be recruited through the neurology clinic in Houston using phone, email or postal communications. People who are interested in taking part will be contacted by the research team via phone or email and explained the study in detail. If the selection criteria are met, informed consent forms and participant information leaflets will be sent via post or email, or obtained during a routine clinic visit.

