- Participants will be **randomly allocated in blocks** to either the intervention or control group, and the allocation group will be **concealed from the study personnel** that are analyzing the data.

Study Procedures

- Subjects in the intervention group will receive a Samsung Windows Mixed Reality headset with motion controllers that links to their PC/laptop. They will be given 3 different VR video games (Box VR, Beat Saber and The Climb) at onset. They will be instructed to play a minimum of 3 sessions per week, one session on each game, for the first 3 months. They will have the possibility of dropping one game for the remaining 3 months but maintaining a minimum of 3 sessions per week. Each session will last 45 minutes. They may play more than 3 sessions per week but will be required to document additional time.
- **Exercise logs** will be provided to document weekly sessions for monitoring adherence. Participants in both groups will be asked to document any sport activities performed during the study period, with an estimate of duration per week and type of activity, to account for physical activity done outside of the active intervention. This will be recorded during the 6-month intervention period.
- The intervention group will also receive two **education discussion sessions** on the benefits of exercise for people with MS. The investigator MS specialists will conduct these sessions either by phone or at the time of a clinic visit and will also discuss difficulties encountered by participants with adherence.
- A neuropsychologist or MS specialist will perform an **objective cognitive assessment** at the time of enrollment, at 6 months and at 12 months follow-up, consisting of the **Brief International Cognitive Assessment for MS (BICAMS)**, which includes three subtests:
 - **Symbol Digit Modalities Test (SDMT)**, a measure of sustained attention, working memory and information processing speed
 - **California Verbal Learning test – II (CVLT-II)**, a measure of verbal memory (immediate recall) including the first 5 recall trials
 - **Brief Visuospatial Memory Test (BVMT) - Revised**, a measure of visuo-spatial learning and delayed recall, using the first 3 recall trials

The battery takes 15 min to complete, requires no specialist equipment and no specialist expertise in cognitive assessment.

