- **Subjective assessments** will be distributed to all participants (exercise intervention group and control group) in weeks 1 and 12 of study enrollment, and at 6-month and 12-month follow-up. The time allocated to complete these assessments is estimated to be 15-20 minutes for each visit. These will include:
 - **Multiple Sclerosis Impact Scale-29 (MSIS-29)**: 29-item self-report measuring the physical and psychological impact of MS from the patient's perspective during the previous 2 weeks.
 - **Modified Fatigue Impact Scale (MFIS)**: 21-item self-report measuring the impact of fatigue on physical, cognitive and psychosocial aspects of MS during the previous 4 weeks.
 - **Hospital Anxiety and Depression Scale (HADS)**: 14-item self-report measuring the degree of anxiety and depression in participants during the previous week.
- An MS specialist will perform a pre- and post- **objective motor assessment** during a routine clinic visit at the time of study enrollment, at 6 months and 12 months follow-up. This assessment will include:
 - **Six Minute Walk Test (6MWT)**: the participant is instructed to walk for six minutes as quickly and safely as possible and the distance covered will be recorded. This test has demonstrated excellent test-retest reliability and validity among people with mild to moderate MS²³.
- Study personnel will collect assessments during routine clinic visits using allocated forms that will be identifiable by date and subject study code number. An investigator blinded to group allocation will subsequently analyze the data.

Budget and financing

- This study has funding from Microsoft and from a private sponsor.
- Cost of VR headset and motion controllers from Microsoft : model Samsung HMD Odyssey+ Windows (\$199.00 per unit, total of 15 units for the intervention group = \$2'761.12)
- The Windows Mixed Reality headsets are compatible with a PC that will run Windows 10 Fall Creators Update, requiring no further participant equipment.
- Cost of the 3 VR video games: Box VR \$19.99, Beat Saber \$19.99, The Climb \$9.99 (downloaded from STEAM stores) – total of \$49.97 per subject, total of \$600 for the intervention group.
- Additional funding is also available with assistance from Microsoft for software to support minimum system requirements for the selected VR exercise games.

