- The subjective assessments will be mailed to the participants or given when seen in clinic. Study staff will perform the 6MWT at the time of a routine clinic visit and will require no additional costs.
- The three cognitive assessments per subject will be carried out by a qualified neuropsychologist or neurologist and will be performed at the time of a routine clinic visit.

Data and Safety Monitoring

- During the course of study participation, subjects might experience an adverse event related to the physical activity or to their underlying MS. These events might include falls, musculoskeletal injuries, neurological symptoms suggestive of a clinical relapse, or any other physical or psychological cause of distress. These events will be documented by participant self-reports and contacting study personnel. They will be graded from 1 to 3 according to their degree of severity with 1 = mild, no interference with daily activities, 2 = moderate, some interference with daily activities and 3 = severe, significant interference with daily activities and requiring medical intervention.
- The research team will perform a **periodic review of adverse events** recorded once every 2 months as well as an assessment of adherence to the exercise programs and any other concerns raised by the research team or the participants.
- In the event of a clinical relapse or worsening of a participant's neurological symptoms, the research team will promptly inform the MS specialist in charge of that participant's care. Subject's participation in the intervention group will cease.

Statistics

- Statistical analysis will be performed using the software program **Stata version 15**.
- Descriptive numerical or graphical summaries will be used for demographic and clinical characteristics of the sample population at baseline. Independent samples t-tests and chi-square tests will be done to assess differences between intervention and control groups on pre-trial and post-trial assessments. Only participants who completed the 6-month exercise program will be included in the analysis of the intervention group but missing data will be noted. Paired sample t-tests and chi-square tests will be conducted to determine differences in pre-trial and post-trial assessments within each group. If data reveals a skewed distribution, Kruskall Wallis tests will be used for continuous variables. All tests will be conducted using an alpha = 0.05 level of statistical significance.

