- Qualitative analysis will be performed through a survey questionnaire collected at the time of the 6-month follow-up, to determine participants' experience and longer term perspectives with regards to the integration of physical activity in the management of their disease.
- The selection of subjects to be included in the analyses will comprise all of those randomized to the control group and all of those randomized to the intervention group who completed the 12-week

exercise program. Dropouts at all stages (enrollment, randomization, intervention, 6-month follow-up) will be recorded.

Ethics

- IRB approval will be sought from CPHS prior to initiation of this study.
- Prior to enrollment in the study, all subjects and parents will be explained all parts of the research in a detailed manner by one of the study investigators. This will be conducted in a quiet environment either at the UT Clinic or by phone. Participants will be given the opportunity to ask questions during the consent process and at any time for the duration of the study. There will be no time limit to obtaining patient consent. Subjects will also be allowed to withdraw their consent at any time by contacting one of the study's investigators.

Data handling and record keeping

- Upon obtaining informed consent from each participant and all selection criteria met, study personnel will access demographic characteristics and all clinical data relevant to MS. This will include past and current disease-modifying therapies (DMTs), symptomatic treatments, EDSS score at enrollment time, burden of disease on MR imagery as well as quantitative information on the degree of physical activity at the time of enrollment.
- All information obtained during the study will be stored on a password-access database that can only be viewed and modified by the PI and co-investigators.
- All subjects enrolled in the study will be attributed a coded number and all personnel information will be de-identified upon collection. The subject codes will be maintained by study staff within the secure database only accessible by study staff and on UT Health-supported servers approved for storing PHI.

Quality control and assurance

- Staff investigators will conduct the subjective and objective assessments. All assessors will be blinded to subject group allocation and subjects will be instructed not to inform them of their allocated group.

Publication Plan

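### No planned comparison of the arms uses the baseline scores the trial collects; with all 24 analyzed, a prespecified ANCOVA would on average narrow the 95% CI once the baseline-to-6-month correlation exceeds about 0.22 to 0.23

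*Combined protocol and SAP*

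**What the plan says.** For continuous outcomes the Statistics section gives one between-group method: "Independent samples t-tests and chi-square tests will be done to assess differences between intervention and control groups on pre-trial and post-trial assessments". Kruskal-Wallis is the fallback for skewed data. Paired tests of pre-trial against post-trial scores are planned within each group. Neither a covariate nor a model nor a between-group comparison of change appears.

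The baseline scores exist. Under Study Procedures, BICAMS (SDMT, CVLT-II, BVMT-R) is given "at the time of enrollment, at 6 months and at 12 months follow-up", the 6MWT "during a routine clinic visit at the time of study enrollment, at 6 months and 12 months follow-up", and the questionnaires (MSIS-29, MFIS, HADS) "in weeks 1 and 12 of study enrollment, and at 6-month and 12-month follow-up". Study Design puts the first assessment earlier: "a series of subjective and objective assessments will be performed prior to onset".

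Two further points bear on the analysis. The term post-trial is not defined, although Study Design lists "pre- and post- assessments performed at onset, 3 months, 6 months and 12 months follow-up"; I take it as 6 months. The analysis set is also not everyone randomized. One sentence reads "Only participants who completed the 6-month exercise program will be included in the analysis of the intervention group". Another keeps "all of those randomized to the control group and all of those randomized to the intervention group who completed the 12-week" program.

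**The concern.** The null hypothesis under Objectives is a contrast between the arms, and none of the planned tests of that contrast conditions on where participants started. A significance test on pre-trial scores adjusts nothing in the post-trial comparison. A paired test within one arm measures change in that arm, including practice effects and natural course, and says nothing directly about the difference between arms.

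Precision is what is at stake. With 12 per arm the unadjusted 95% CI is about ±0.84 SD. Variation between participants that was already present at baseline stays in the error term, although the trial has the data to remove some of it.

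**Working it through.** **Inputs from the documents.** 12 per arm, 24 in total (Study Design); alpha 0.05 (Statistics); two-sided (Objectives); unadjusted t-test (Statistics).

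**Inputs assumed.** The baseline-to-6-month correlation r is not given, so a range is shown. The SD is not given, so results are in SD units. Scores are taken as normal with a common linear slope and equal variances, and all 24 have a 6-month score.

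**The plan's own figure.** The sample size of 24 comes with no effect size, SD or power, so it cannot be reproduced. For orientation, 12 per arm detects 1.20 SD with 80% power using the t-test.

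**Unadjusted t-test.** Half-width = t(0.975, 22) × √(2/12) = 2.0739 × 0.4082 = 0.847 SD. Averaged over the sampling of the SD, this is 0.837.

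**ANCOVA.** Half-width = t(0.975, 21) × √[(2/12)(1 − r²)(1 + 1/(N − 4))]. With N = 24 the last factor is 1 + 1/20 = 1.05, the expected price of chance baseline imbalance. So half-width = 2.0796 × 0.4082 × √1.05 × √(1 − r²) = 0.870 × √(1 − r²).

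| r | ANCOVA half-width (SD) | Ratio to t-test | Simulated power at 0.8 SD |
|---|---|---|---|
| 0 | 0.870 | 1.027 | 45% |
| 0.3 | 0.830 | 0.980 | 48% |
| 0.5 | 0.753 | 0.890 | 56% |
| 0.7 | 0.621 | 0.734 | 73% |
| 0.8 | 0.522 | 0.617 | 86% |

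The t-test has 46 to 47% power at 0.8 SD (100,000 simulated trials per cell). At 0.5 SD it has 21 to 22%, and ANCOVA has 21 / 22 / 26 / 36 / 48% over the same values of r.

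**Break-even.**
- Standard error alone: r = √(1 − 20/21) = 0.218.
- Mean CI half-width: 0.225.
- Root-mean-square half-width: 1 − r² = (2.0739/2.0796)²/1.05, so r = 0.230.

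In 200,000 simulated trials per value of r, the ratio of mean widths was 1.002 at r = 0.22, 0.999 at 0.23, 0.889 at 0.5 and 0.733 at 0.7.

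**Fewer intervention scores.** With 10, 8 or 6 intervention participants against 12 controls, the break-even on mean half-width is 0.238, 0.252 or 0.270.

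**Cost at r = 0.** √1.05 = 1.025 from imbalance, times 2.0796/2.0739 = 1.003 from the lost degree of freedom: about 3% wider.

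**Skewed scores** (lognormal, skewness 1.75, shift 0.8 SD, 12 vs 12; r = 0 / 0.3 / 0.5 / 0.7 / 0.8). Kruskal-Wallis has 61 to 62% power and rank-based ANCOVA 59 / 62 / 70 / 82 / 91%. A score-unit ANCOVA tested by permutation has 50 / 53 / 60 / 74 / 85%. In separate checks on skewed data, a percentile bootstrap of the ANCOVA difference covered only about 92 to 93%, while the ordinary ANCOVA interval covered about 95%.

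**The case against.** The strongest reply is that this concerns efficiency and not error, and that the gain depends on a correlation the documents never give. Their one statement on reliability is qualitative and concerns the 6MWT, a secondary outcome. Both points stand. A reader might infer that the planned t-test is invalid. On a set of all randomized participants it is not: simulated null rejection was 0.049 to 0.051 for both methods.

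A reader might also infer that ANCOVA narrows the interval in any given trial above the threshold. The narrowing is only on average: the ANCOVA interval was the shorter one in about 39% of simulated trials at r = 0.22, 86% at 0.5 and 99% at 0.7. Nor does adjustment rescue a moderate effect, as the power at 0.5 SD shows.

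A further objection is that the threshold describes an analysis the plan does not contain, because the intervention arm is limited to completers. That also stands, and it rules out reading ANCOVA as a cure for the rule. Adjustment removes the bias if completion depends only on baseline. It does not if completion depends on the part of the 6-month score that baseline leaves unexplained. In an assumed example (no true effect, 9 of 12 kept, completion correlated 0.6 with that part, r = 0.5), both methods were biased by 0.20 SD, with type I error 7.6% for the t-test and 8.2% for ANCOVA.

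Finally, with skewed data the score-unit ANCOVA tested by permutation has less power than Kruskal-Wallis below r of about 0.5. The threshold of 0.22 to 0.23 therefore does not carry over to power in that case.

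**Conclusion.** The concern holds as an avoidable loss of precision. No planned comparison of the arms uses baseline, and including it costs little. With all 24 analyzed and normal scores, the trade is lopsided: at worst about 3% wider (r = 0), and about 11% narrower at 0.5 or 27% at 0.7. The break-even of 0.22 to 0.23 follows from the sample size, and rises to about 0.24 to 0.27 if only 10 to 6 intervention participants have scores. Where any outcome sits on that range is an assumption. The documents do not support calling the unadjusted test wrong on the full randomized set, or promising a gain of a particular size for BICAMS. The change is worth making before the data are examined, since choosing between adjusted and unadjusted results afterwards invites selection.

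**What to change.** - **Main analysis.** For each continuous outcome (SDMT, CVLT-II, BVMT-R, 6MWT, MSIS-29, MFIS, HADS), prespecify an ANCOVA of the 6-month score on group and the baseline value of the same score. Report the adjusted difference with its 95% CI, and define post-trial as the 6-month assessment.
- **Analysis set.** Apply it to all randomized participants with a 6-month score, and state how missing 6-month scores are handled.
- **Skewed scores.** Keep the ANCOVA estimate and its model-based interval. Use rank-based ANCOVA as the supporting test in place of Kruskal-Wallis. Do not use a percentile bootstrap interval at 12 per arm.
- **Pre-trial scores.** Use them as covariates and descriptively, without significance tests between arms.
- **Timing.** Take every baseline score before randomization. Reconcile the questionnaire timing in Study Design (before onset) with that in Study Procedures (week 1), and state the order of enrollment assessments and randomization for BICAMS and the 6MWT.
- **Separately.** Correct the completers-only rule and its conflict between a 6-month and a 12-week program. This point also leaves open which BICAMS subtest is primary and how three tests at 0.05 are handled.

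Cost: SAP wording and one regression command in the software already named. No extra participants or measurements are needed. The week-1 questionnaires may have to move ahead of randomization, and the CI is about 3% wider if the correlation is zero.

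### The analysis keeps every randomized control but only intervention completers, and defines completion in two conflicting ways, so the BICAMS comparison is no longer between the randomized groups

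*Combined protocol and SAP*

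**What the plan says.** Two bullets in the Statistics section define who is analysed. The first says: "Only participants who completed the 6-month exercise program will be included in the analysis of the intervention group", and adds that missing data will be noted. The last gives the analysis set as follows: "all of those randomized to the control group and all of those randomized to the intervention group who completed the 12-week". The period it names is the length of the programme, and it adds only that dropouts are to be recorded.

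Four other places bear on this:

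- **Study Design** sets the length of the programme: "The study will be conducted over one year with 6 months of intervention". Study Procedures agrees, describing a first and a second block of 3 months.
- **Data and Safety Monitoring** says that after a clinical relapse or worsening of neurological symptoms, "Subject's participation in the intervention group will cease". Controls have no corresponding exit.
- **Study Procedures** schedules BICAMS "at the time of enrollment, at 6 months and at 12 months follow-up", and the questionnaires "in weeks 1 and 12 of study enrollment, and at 6-month and 12-month follow-up".
- **Objectives** frames the null hypothesis around participants enrolled in the programme versus routine care, two-sided. It also lists a secondary objective: "To determine the number of clinical relapses and new T2 MRI lesions (brain").

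Nowhere do the documents plan an analysis of all randomized participants, a method for missing outcomes, or a sensitivity analysis.

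**The concern.** Completing the programme happens after randomization and can depend on how the participant is doing. Selecting on it in one arm only means the analysed intervention group is a subset chosen by its own course, set against an unselected control group. The hypothesis concerns those enrolled; the analysis concerns those who finished.

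The two definitions also produce different data sets. A participant who stops in month 4 is excluded under the 6-month rule and included under the 12-week rule. With 12 per arm, one or two such people matter. Nothing says which rule governs, so the choice could be made after results are known. Neither bullet says how many sessions count as completion.

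At stake is whether a difference in BICAMS can be attributed to the VR programme. If the same analysis set is used for relapses, any comparison of relapse counts between arms is distorted too, although relapse symptoms would still be captured as adverse events.

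**Working it through.** **Is there a figure in the plan to reproduce?** No. The plan gives 24 participants, 12 per group, alpha 0.05 two-sided and an independent-samples t-test. It gives no effect size, SD, power, drop-out rate or relapse rate. Everything below except those inputs is an assumption, used only to show the order of magnitude. Scores are in SD units, higher is better, and there is no true effect. Error rates are for one score and one t-test.

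**General identity.** If a share *e* of the intervention arm is excluded and all controls are kept,

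bias = *e* × (mean of completers − mean of excluded).

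For 3 of 12 excluded and a gap of 1 SD: 0.25 × 1 = 0.25 SD. With no gap the bias is zero, and if better performers stop it is negative.

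**A. The relapse rule alone.** This is the one outcome-related exit written in the plan. Assume a 6-month relapse risk *r* = 20% in both arms at a constant rate over 26 weeks, and a score lowered by *d* SD after a relapse. A relapser is taken to be a non-completer if the relapse precedes the completion point.

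- *6-month rule.* No relapsers remain in the intervention arm; controls keep *r*. Bias = *r* × *d* = 0.20 × 0.5 = 0.10 SD to 0.20 × 1.0 = 0.20 SD.
- *12-week rule.* Risk by week 12 is 1 − 0.8^(12/26) = 0.098. Risk in weeks 12–26 is 0.200 − 0.098 = 0.102. The relapser share among those retained is 0.102 / 0.902 = 0.113. Bias = (0.200 − 0.113) × *d* = 0.087*d*, or 0.04 to 0.09 SD.
- *Expected relapsers analysed.* Controls: 12 × 0.20 = 2.4. Intervention: 0 under the 6-month rule, 12 × 0.102 = 1.2 under the 12-week rule.
- *Simulated type I error.* 6-month rule 5.4–6.8%; 12-week rule 5.1–5.4%; all randomized, about 5%.
- *Range.* Over *r* = 10–40% and *d* = 0.5–1.0, the bias is 0.05–0.40 SD (6-month) against 0.02–0.16 SD (12-week). It is zero if relapse does not affect the score.

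**B. Wider prognosis-related drop-out.** In 200,000 simulated trials per scenario, the lowest *q* of 12 intervention participants on a latent prognosis variable are dropped and all controls are kept. The correlation is between that variable and the outcome.

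| Dropped | Correlation | Bias (SD) | Type I error |
|---|---|---|---|
| 3 | −0.3 | −0.12 | 5.8% |
| 3 | 0 | 0 | 5.0% |
| 1 | 0.3 | 0.05 | 5.1% |
| 3 | 0.3 | 0.12 | 5.8% |
| 3 | 0.5 | 0.20 | 7.5% |
| 3 | 0.7 | 0.28 | 10% |
| 4 | 0.7 | 0.36 | 12.5% |

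If 2 controls are lost in the same way against 3 intervention participants, the bias falls to 0.03–0.08 SD and the error to 5.3–7.0% (correlation 0.3–0.7). If losses are equal, the bias is zero.

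**Precision.** Analysing everyone does not cost power through numbers. The difference detectable with 80% power is 1.20 SD for 12 v 12, against 1.30 SD for 12 controls and 9 completers (noncentral t).

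**The case against.** The strongest case against concerns size and direction. The largest figures need 4 of 12 to stop, exactly those with the worst prognosis, a correlation of 0.7 and complete control follow-up; the documents support none of these. The only documented mechanism, the relapse rule, gives at 20% risk a bias of at most 0.20 SD, under half the standard error of a 12 v 9 comparison (√(1/12 + 1/9) = 0.44 SD). Some stopping may have nothing to do with prognosis: the plan itself foresees equipment trouble ("Microsoft will also provide customer service for any technical difficulties with the VR headsets provided"). If better-functioning participants stop, the bias runs against VR. All this stands, and it is why the direction is only likely.

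Further points stand in part:

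- Twelve weeks may refer to the first 3-month block of the programme, after which a game may be dropped. That may explain the wording, but the two rules still conflict.
- The analyst is to be blinded to allocation. This limits selective choice of a rule but does not remove it, because a filter applied to one arm cannot be applied without knowing the arm.
- The plan does not say outright that a relapser counts as a non-completer, or that relapses will be compared between groups. Both are natural readings, not stated facts.
- BICAMS has three subtests and two post-baseline times, so the error rates above describe a single test, not the whole primary objective.

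None of these supplies an analysis of all randomized participants or reconciles the definitions. Noting missing data and recording dropouts does not restore the comparison.

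**Conclusion.** The concern holds, and it must be fixed before the analysis. As written, the plan compares all randomized controls with a self-selected part of the intervention arm, under two incompatible definitions of completion. That rests on the text alone and needs no assumption about numbers.

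The size cannot be derived from the documents. Under the assumptions shown, the relapse rule alone gives a modest bias towards VR and little inflation of the error rate. Broader prognosis-related drop-out could roughly double the nominal 5% or somewhat more. Uninformative stopping gives no bias, and selective stopping by better performers reverses it. The trial could not establish from its own data which case applied.

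**What to change.** Replace the two Statistics sentences with one rule: the primary analysis includes all randomized participants in the group to which they were allocated, whatever their adherence. Then:

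- Continue the scheduled 6- and 12-month BICAMS, 6MWT and questionnaires, and the relapse counts, in those who stop exercising, with MRI on whatever schedule the trial uses. The clinical stopping rule is not changed by this.
- State one missing-data method, applied alike to both arms, and a sensitivity analysis to it.
- Reconcile the 6-month and 12-week wording. Keep any completer analysis as supplementary, with a single definition of completion fixed before the data are seen.

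The cost is the rewording plus some extra effort to follow those who stop, at visits already planned for BICAMS, 6MWT and the questionnaires. The text gives no MRI schedule, so an MRI cost cannot be stated. The estimated effect may be smaller than among completers. The change should be made early, because assessments not collected after someone stops cannot be recovered.
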